6. STUDY DESIGN SUMMARY

6.1 Summary of Trial Design

This study will employ both qualitative and quantitative measures in order to evaluate the resources required to implement routine lung function testing for children in primary care; and to investigate the impact this would have on diagnosis in children with suspected or presumed asthma. In total we hope to recruit between 3-6 GP sites across Leicestershire and Northamptonshire for the study, which would represent a patient population of ~120,000-150,000 people, representing 1500-2000 children potentially eligible to take part in the study based on our preliminary data. Primary care sites will be approached by the study team with assistance from the CCG R+D manager for Leicester ([name]) and the CRN locality manager for East Midlands ([name]). We aim to recruit sites of differing sizes and with different patient demographics.

Site survey questionnaires will be completed for each site by the study team to gather information about the individual practice's patient population and current asthma review set up. Readiness for change questionnaires will be used to investigate staff opinions, concerns and perceived barriers to implementation. These will be sent out to GPs, practice nurses, HCAs and practice managers at each participating site. The study team will develop and refine a package of training and support which will be based on an existing training programme for primary care practitioners to perform spirometry on adult patients with COPD in Leicestershire primary care practices. We will evaluate the success of the training by supporting and monitoring the primary care practitioners utilising these tests in primary care asthma review clinics. The length of training required in order for different staff groups to be able to perform spirometry and FeNO testing independently will be documented.

To investigate the impact of implementing lung function testing for children into primary care, we will consent children onto the study for the purposes of accessing their electronic records (see below for details) and a follow up postal questionnaire only. All children between the ages of 5-16 years inclusive who meet the inclusion criteria (see below) and who are registered patients at the study sites are eligible for recruitment onto the study; we aim to recruit 1000 children based on a 50-70% response rate. We anticipate that the study will last 2 years from beginning to end, which will include time for data analysis and publication of results. This is an outline of the proposed study plan -

Please see Appendix for Gantt chart detailing anticipated duration of study periods.

The study interventions are described in detail below:

Firstly, the study team will meet with interested GP practices to present an overview of the study. The participating practice teams are then expected to complete readiness for change questionnaires and assist the study team in completing the site survey questionnaires in order for the study team to identify training and capacity needs and potential barriers to implementation. Secondly, designated staff (PNS/HCAs) at each practice are expected to complete a package of training aimed at helping them achieve competencies to be able to deliver lung function testing to children independently.

The GPs will then be asked to perform searches of their electronic records to identify children who require or who would benefit from an asthma review based on the inclusion criteria detailed below. The GP practices will then send out clinic appointment letters to these children inviting them to book into an asthma review clinic. The letters from the GPs will make the families aware that they will also be invited to take part in the CHAMPIONS study in addition to their routine review and lung function tests. A patient information sheet will be included with the letters which the GPs send out.

On the day of the clinic, a member of the study team will introduce themselves to the parent and child prior to the appointment in order to give further information about the study, answer questions and to take written consent from those families who wish to participate. It will be made clear that they are welcome to the asthma review and lung function tests whether they choose to consent to the study or not.

For consented patients, the only additional study interventions are 1) the initial health economics questionnaires (CHU9D and PAQLQ), 2) the follow up postal health economics and asthma quality control questionnaires, and 3) allowing us access to their medical records to collect data as detailed below.

Data analysis will be performed using statistical methods described below.

We intend for the results derived from this study to be presented at scientific meetings and published in medical journals and asthma websites. A plain language summary will also be published online which families will be able to access. No identifiable data of any child will be included in any report or publication.

6.2 Primary and Secondary Endpoints

The primary end point to this study will be when designated healthcare staff at each participating GP practice are able to independently and competently perform and interpret objective lung function tests; and have done so on all the children with suspected/presumed asthma on their patient register who have agreed to attend an asthma review clinic.

The secondary endpoint is when we have developed and refined a training and support package for primary care staff in the use of spirometry and FeNO testing in children; that is both acceptable to end-users and sustainable by the team delivering the training.

7. STUDY PARTICIPANTS

7.1 Overall Description of Study Participants

Children with asthma or who have suspected asthma managed in primary care.

7.2 Inclusion Criteria

Male or Female, aged 5-16 years who are:

1. On the practice asthma register or
2. Are prescribed regular (on repeat prescription) inhaled corticosteroids including beclometasone, fluticasone and budesonide and also search specifically for 'brands' that are commonly prescribed to include 'clenil', 'seretide', 'symbicort', and 'qvar' or
3. Have been prescribed ≥ 2 Salbutamol MDI's in the last 12 months or
4. Had a documented exacerbation of asthma in the last 12 months
5. Able and willing, in the opinion of the Investigator, to give informed consent

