4. BACKGROUND AND RATIONALE

In the UK the latest figures indicate that a total of 4.1 million people receive treatment for asthma (1). Of these approximately 1.1 million are children over the age of 5 years, which is the equivalent of one in ten children in the UK (2).

Despite the common nature of asthma there is no gold standard test available to diagnose the condition. The diagnosis is generally based on a thorough clinical history taken by an experienced clinician. Studies in adult populations however suggest that many are misdiagnosed including over and under-diagnosis of asthma (3-6). Over-diagnosis may affect up to 30% of adults diagnosed with asthma (3) and can result in inappropriate and unnecessary use of asthma medications and increased healthcare costs. Under-diagnosis often results in poor control and reduced quality of life.

Under-diagnosis and under-treatment of childhood asthma in primary care have been reported from several European countries (7-8) including the UK (9). The International Study of Asthma and Allergies in Childhood (ISAAC) for example reported that one-third of children aged 12 to 14 years in Great Britain with frequent night time wheezing had no diagnosis of asthma (9). Getting the diagnosis right in children is important because children have the highest asthma hospital admission rates for any age-group with asthma and under-diagnosis is associated with poor asthma control. Moreover, inappropriate treatment of children who do not have asthma with asthma medications can lead to unnecessary side-effects including a decreased growth velocity resulting from long-term inhaled corticosteroid use.

A recent draft NICE guideline (10) for asthma diagnosis and monitoring, originally due for publication in July 2015, recommends the use of objective tests including spirometry and FeNO testing to diagnose asthma in all patients 5 years and older under investigation for asthma. Recent BTS/SIGN asthma guidelines published in October 2014 also state that spirometry is superior to peak flow measurements, currently the most widely used lung function test in primary care in the management of asthma (11).

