Proposed NICE asthma diagnostic algorithm: For children aged 5 to 16 years and adults with symptoms of asthma the draft guideline recommends spirometry testing for diagnosis and where obstructive spirometry is present bronchodilator reversibility should be considered. FeNO, an inflammatory marker in exhaled breath linked with asthma, should be considered where spirometry is normal and where obstructive spirometry does not reverse with bronchodilators. The proposed NICE guidance for diagnosis of asthma is summarised below.

[figure not shown]
Diagnostic criteria for asthma in children aged 5-16 years:

- Clinical symptoms compatible with the diagnosis

- Objective tests including
 - Obstructive spirometry
 - Reversibility following short acting beta-2-agonists ($\geq 12\%$ increase in FEV₁)
 - Raised FeNO (≥ 35 ppb)
 - Peak flow variability ($>20\%$)

No single positive test is diagnostic for asthma

Draft NICE diagnostic algorithm for children aged 5-16 years with suspected asthma

Asthma monitoring: Spirometry should be done in adults with asthma and considered in children at every asthma review.

Spirometry: Spirometry is available in primary care and performed in adults with COPD where it is already part of the Quality Outcome Framework (QOF). NICE and BTS/SIGN state that spirometry is preferable to measurement of peak expiratory flow because it allows clearer identification of airflow obstruction, and the results are less dependent on effort.

Spirometry is however only rarely performed in children in primary care. Children benefit from visual incentive spirometry which requires a special spirometer usually not available in GP

practices. Interpretation of spirometry in children also requires a slightly different approach. Consequently, practice nurses/health care assistants (PN/HCA) usually have no experience in performing and interpreting spirometry in children, but could be trained to do so. The amount of training required and how best to deliver it are currently not known and addressing these knowledge gaps is one of the main implementation research questions.

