The use of the lung function tests in children is already routinely done in hospitals, has been shown to be safe in children and is now being recommended (at least in draft guidance) by NICE. As such, our research question is not whether we should use spirometry and FeNO testing in primary care, indeed they are not viewed as research interventions in this study; the question is – how can this be achieved?

Therefore the primary rationale for this study is to identify the training needs and capacity requirements of primary care practices in order for objective lung function testing to be made available for all children with suspected or confirmed asthma cared for in the non-hospital setting.

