5. OBJECTIVES

5.1 Primary Objectives

The main objective for this study will be to evaluate the training and capacity requirements of primary care sites in order for them to be able to deliver routine spirometry and FeNO testing for children with suspected or presumed asthma.

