8.2 Screening and Eligibility Assessment

Children who clinically warrant an asthma review, which are also our potential participants, will be identified by the direct care team from participating GP sites. The direct care team will search their practice electronic database for children who meet the inclusion criteria using age limits "5 to 16 years," and to include children who are either on the asthma register or based on asthma medications prescribed as detailed in the inclusion criteria above.

Once identified, the direct care team will send by post the standardised PIS along with the asthma review invitation letters to families. The invitation letter will invite families to phone the GP practice to book onto an asthma review clinic. We anticipate that there will be a minimum of 1 week between the time families receive PIS and the next available asthma review clinic.

Demographics

The date of birth, gender, race, primary language and country of birth will be recorded by the research team in the CRF following written consent at the asthma review.

Medical History

Details of length of asthma diagnosis or duration of “asthma” symptoms will be recorded at time of asthma review by study team following written consent along with concomitant medication and any physical examination (detailed below).

Concomitant Medication

All prescription “asthma” medications (bronchodilators, inhaled steroids, leukotriene receptor antagonists etc.) will be recorded on CRFs and assigned to a corresponding asthma treatment step as detailed in BTS/SIGN asthma guidelines. We will also record number of days of oral steroids prescribed in the preceding 6 months.

Physical Examination

Height and weight of participating children will be recorded.

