20. APPENDIX A: STUDY GANTT CHART

Study Task	Time in Months							
	-3	-6	-9	-12	-15	-18	-21	-24
Identify Participating Practices								
Site Survey and Change Readiness Questionnaires								
Develop training package								
Delivery of training package to healthcare workers performing the test								
Identification of patients under investigation/review for asthma								
Perform asthma reviews								
Review and refine training package								
Collection of health outcome data								
Quantitative and qualitative data analysis								
Dissemination and publication of study results

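### The objectives speak for all children with suspected asthma, but entry misses new, little-treated suspects, so the session estimate and diagnosis counts describe a narrower group

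*Combined protocol and SAP*

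**What the plan says.** **Population stated.** The primary objective (Section 5.1) asks what practices need in order to "deliver routine spirometry and FeNO testing for children with suspected or presumed asthma". The rationale in Section 4 wants testing available "for all children with suspected or confirmed asthma cared for in the non-hospital setting". The primary endpoint (Section 6.2) requires tests on "all the children with suspected/presumed asthma on their patient register who have agreed to attend an asthma review clinic". Section 7.1 also counts suspected asthma among the participants. The background describes the guideline being implemented in these terms: "For children aged 5 to 16 years and adults with symptoms of asthma the draft guideline recommends spirometry testing for diagnosis". A task in the Gantt chart (Appendix A) is "Identification of patients under investigation/review for asthma".

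**Population admitted.** Section 7.2 lists four alternative routes, the first being "On the practice asthma register or". The second is an inhaled corticosteroid on repeat prescription, the third at least two salbutamol inhalers in 12 months, and the fourth a documented asthma exacerbation in 12 months. The fifth item is consent. Section 8.2 tells practices to search for children who meet these criteria, and then names the terms: "to include children who are either on the asthma register or based on asthma medications prescribed as detailed in the inclusion criteria above".

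**Use of the results.** Section 9.1 (Capacity Requirements) times each test, counts the patients who can be reviewed per session, and from these derives how many sessions a typical practice would have to support. Section 5.2 counts confirmed diagnoses and misdiagnoses.

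**The concern.** The group described in the aims is wider than the group the criteria let in. A child who has recently presented with symptoms, is not on the register and has had little or no treatment is within the guideline's diagnostic pathway and within the wording of Section 5.1. Nothing in Section 7.2 brings that child in. Sections 6.1, 8.1 and 8.2 describe recruitment only through the practice search, with no route by symptom record or clinician referral.

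Two outputs are affected. A practice or commissioner reading the session estimate would take it as the demand created by the guideline, when the demand from new work-ups has not been counted. The diagnosis results would also be read as covering under-diagnosis, which Section 4 gives as part of the motive for the study: "one-third of children aged 12 to 14 years in Great Britain with frequent night time wheezing had no diagnosis of asthma". The endpoint in Section 6.2 would not reveal the gap, because a child who is never invited cannot agree to attend. The endpoint can therefore be met without these children.

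**Working it through.** **1. The plan's own figure.** Inputs: a pool of 1500-2000 eligible children from a population of 120,000-150,000 (Section 6.1), and a response rate of 50-70% (Sections 6.1 and 11.2). The formula is pool × response rate.

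- 1500 × 0.50 = 750
- 2000 × 0.50 = 1000
- 1500 × 0.70 = 1050
- 2000 × 0.70 = 1400

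The target of 1000 is reproduced by 2000 × 0.50 and lies within the range 750-1400. The pool is 1500/120,000 = 1.25% to 2000/150,000 = 1.33% of the population. Section 11.2 bases the target on children expected to meet the inclusion criteria, together with team capacity. It is a feasibility figure, and it neither supports nor contradicts this point.

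**2. The routes against a test case.** Take a child aged 5-16 with new symptoms, no register entry, no repeat inhaled steroid, no or one salbutamol inhaler, and no documented exacerbation.

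| Route in Section 7.2 | Met? |
|---|---|
| Asthma register | No |
| Repeat inhaled corticosteroid | No |
| At least 2 salbutamol inhalers in 12 months | No (0 or 1) |
| Documented exacerbation in 12 months | No |

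The child meets 0 of 4 routes, yet fits Sections 5.1 and 7.1.

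**3. What the routes do reach.** In the preliminary data (Section 4), counting children on regular inhaled steroids or with at least two short-acting inhalers brought the total to about 4 times the register. On that figure 1 − 1/4 = 75% of the pool is off the register. Entry is therefore far from limited to labelled children. Section 4 warns that the sample was small and may not generalise.

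**4. Where the gap enters the session estimate.** Let *p* be patients per session, *D* the children who attend through the Section 7.2 routes, and *U* the other new suspects who would attend for testing. The demand implied by the stated objective is (*D* + *U*)/*p*; the study observes *D* and *p* only. The budget in Section 17 allows 200 sessions, so 1000/200 = 5 children per session if all 1000 are reviewed in them. At that planning ratio, every 5 children in *U* are one session not counted. The documents give no value for *U*, so no corrected total can be computed.

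**5. Section 8.2 against Section 7.2.** The named search terms cover routes 1 to 3. Route 4 is covered only by the general reference to the inclusion criteria in the same sentence.

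**The case against.** The strongest reply is that the search was built to find unlabelled children and does so. The preliminary total was about four times the register and close to the one in ten expected from epidemiology. Two salbutamol inhalers without a register entry is a fair working definition of suspected asthma. The vehicle throughout is the asthma review clinic, the guideline also covers monitoring at review, and the Gantt row mentions review as well as investigation.

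Much of this stands. Many suspected cases are reached, and a register-and-prescription search is a reasoned choice for an implementation study. It does not close the gap. Where Section 4 gives its one-in-ten figure, it derives it from people receiving treatment for asthma, so agreement with it says nothing about children who are not treated.

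Three stronger readings do not hold.

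- A reader might infer that the diagnosis counts lean towards over-diagnosis. This is not shown. Off-register children confirmed by testing would count as newly established diagnoses, and the statement about wheezing children without a diagnosis does not say that they were untreated.
- A reader might infer that the timings are biased. Time per test and patients per session are measured on the children tested and do not change because others were not invited. Only the step up to total sessions is affected.
- A reader might infer that Section 8.2 removes the exacerbation route. It first calls for children who meet the inclusion criteria, so the route remains in force and is at most unnamed.

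**Conclusion.** The mismatch between the stated and the sampled population is real, and it limits what the study can conclude. The stated scope is children with suspected or presumed asthma in general. The sampled scope is children who are registered, treated to the Section 7.2 thresholds, or have a recorded exacerbation. Total session demand from new diagnostic work-ups is not captured, and under-diagnosis can be seen only among children who have already reached one of those thresholds.

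The size is unknown. A reader might put a percentage on the missing group, but nothing in the documents supports one. The conclusion rests on reading the four routes as complete, and no other section adds one. The per-test timings, the training findings and the target of 1000 are unaffected. The Section 8.2 point is one of wording: a search written only from the named terms would miss children who qualify by exacerbation alone.

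**What to change.** 1. In Section 8.2, name an asthma-exacerbation term among the search terms, so that the search matches the fourth route in Section 7.2.
2. Keep entry as it is. Restate Sections 5.1, 5.2 and 6.2 as applying to children registered with, treated for, or with a recorded exacerbation of asthma, and state that under-diagnosis in untreated children is not estimated.
3. In the search the practices already run, obtain an anonymous count of other children aged 5-16 with a new suspected-asthma presentation in the last 12 months who meet none of the four routes, using one code list for all practices. In the capacity analysis of Section 9.1, report total sessions with and without this count, and state the attendance assumed. The plan's own 50-70% could serve as the range.

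The cost is a protocol amendment, one short extra search per practice, a narrower stated scope, and a count that depends on how well practices code. Section 17 already reimburses administrator time for database searches. No extra reviews are needed.

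Widening entry by symptom codes is not proposed. Families who are invited may have the review whether or not they consent (Section 8.1), the yield of such codes is unknown, the target is tied to team capacity (Section 11.2), and the session budget is set at 200 × £100 = £20,000 (Section 17).

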7.3 Exclusion Criteria

1. Children who are unable to perform lung function tests for any reason
2. Children and young people <5 years and >16 years
3. Unable or unwilling, in the opinion of the Investigator, to give informed consent

8. STUDY PROCEDURES

8.1 Informed Consent

Children aged 5 to 16 years who fulfil the inclusion criteria will be identified from electronic searches performed by the practice staff for the purposes of inviting them for an asthma review. We will provide the practices with patient information sheets (PIS) to post out with the invitation letters sent out by the GPs themselves. The PIS will detail no less than: the exact nature of the study and that the parent is free to withdraw the participant from the study at any time for any reason without prejudice to future care, and that there is no obligation to give consent for access to their child's records in the first place. Even if the parent does not consent to the study, their child is still welcome to the full asthma review including lung function tests as these are part of recommended standard care.

On the day of the clinic, a member of the research team will talk to the family prior to their appointment and explain the study and to answer any questions. The participant will be allowed as much time as wished to consider the information, and the opportunity to question the study team to decide whether they will participate in the study.

It will be made clear that none of the tests performed in the asthma clinic, except the short health economic questionnaires, are part of the research and should be viewed as best practice. We are only seeking consent to: 1) access their child's electronic records in order to obtain information including recent exacerbations and medications prescribed, 2) record answers to a health economic questionnaires onto the CRF, 3) time how long it takes to perform each lung function test and 4) ask their GPs to contact them in 3-6 months' time by post to complete a follow up health economic questionnaire and ACT. Written consent will then be taken from the parents should they agree to participate.

The person who obtains the consent will be suitably qualified and experienced, and have been authorised to do so by the Chief Investigator as detailed on the Delegation of Authority and Signature log for the study. The original signed form will be retained at the study site within Investigator Site File (ISF). A copy of the signed Informed Consent will be given to participants and a copy retained in the participant medical notes. Anyone not medically qualified will undergo UHL consent training.

